13 RISKS TO SUBJECTS

13.1 Foreseeable Risks

Answering questionnaires pose none to minimal risk. In the event a question causes any type of distress, information will be provided to identify psychological resources available to the participant. There is no to minimal risk for providing breath samples for measurement of carbon monoxide (CO). When providing materials to participants by mail, delivery confirmation with signature will be used to confirm the correct person receives the materials.

Cigarette smoking.

Since we are using commercially available cigarettes, the side effects of the cigarettes used in this study would be similar to the use of other commercial cigarette products, including those the participants smoke themselves. Participants could experience an increased risk for mouth sores, gum disease and tooth loss, nausea or stomach aches, vomiting, or high blood pressure. Some people who use cigarettes may experience irritation of the mucosal membranes of the upper respiratory tract (i.e., the membranes that line the mouth and throat), but as the participants in this study are already regular users, we do not think that this is likely to occur.

Roswell Park Protocol Number: I 757820

- Rare but Serious Side Effects: Those that occur in less than 5% of persons who use nicotine products.
 - Mouth irritation
 - Severe sore throat
 - Irregular heartbeat or rapid heartbeat
- More common but less Serious Side Effects: Those that occur in less than 10-30% of persons who use nicotine products.
 - Indigestion or heartburn
 - Nausea, vomiting, dizziness, diarrhea, or weakness

14 POTENTIAL BENEFITS TO SUBJECTS

14.1 Potential Benefits

There are no direct benefits to taking part in this study.

14.2 Indication of No Direct Benefits

There are no direct benefits to taking part in this study. This research has potential to inform FDA regulation of tobacco products.

15 SHARING OF RESULTS WITH SUBJECTS

All analyses will be completed as a group. Though the goal is to publish the overall results in a scientific journal made available to the public, no individual's results or information will be shared either with the subject or public. Participants may receive overall final results of the study by mail if desired.

16 ECONOMIC BURDEN TO SUBJECTS

16.1 Costs that Subjects May be Responsible for Because of Participation in the Research

There are no costs to the participant associated with study participation.

17 PROVISIONS TO PROTECT THE PRIVACY INTERESTS OF SUBJECTS

17.1 Protection of the Subjects' Privacy Interests

Participants will only interact with the research coordinator conducting the interview.

17.2 Steps Taken to Make the Subjects Feel at Ease with the Research Situation in Terms of the Questions Being Asked and the Procedures Being Performed. "At Ease" Does Not Refer to Physical Discomfort, but the Sense of Intrusiveness a Subject Might Experience in Response to Questions, Examinations, and Procedures.

The research coordinators will administer and review an informed consent document, explaining all components of the research study. Participants are only encouraged to verbally agree to the conditions in the consent only if they are completely comfortable with the study design and

Roswell Park Protocol Number: I 757820

procedures. Participants will have the opportunity to ask questions at any point during the study and may withdraw at any time.

17.3 How the Research Team is Permitted to Access Any Sources of Information About the Subjects

The research team is only permitted to access sources of information provided by the participant.

18 VULNERABLE POPULATIONS

N/A.

19 DATA AND SPECIMEN BANKING

19.1 Data Banking

For purposes of this research, we will collect the following identifiable information:

- Participant Name – to verify identification
- Date of birth - to verify age
- Telephone number - to facilitate contact for scheduling
- Mailing address - to send study materials
- Email address - to facilitate contact for scheduling and videoconference access
- Identifiable information will be retained in a separate Excel file from the analytic dataset. The only link to identifiable information will be via a unique ID number.

All questionnaires are administered via REDCap, housed at RPCI. All data files will be electronic, including only the unique subject ID. All datafiles will be stored on the Cancer Prevention server (\CancerPrev\CancerPrev\$\HealthBehavior\TobaccoLab). Access to this folder is restricted to authorized users. Standard protocols for data encryption (via Credant) when using laptops and USB drives will be followed. Twilio is a third-party web service that has been integrated into REDCap to send survey invites and SMS messages to participants via text. All participant data is stored in REDCap, and Twilio is only used to send the text and survey link. When the respondent presses the link, their browser on their smart phone will open to complete the survey in the secure website or read any sent messages. When a participant provides permission for study staff to send the daily survey invite by SMS (text), the Twilio program within REDCap will provide that functionality. When a participant responds, Twilio will relay the information back to REDCap. Once a participant completes a daily survey, the data are sent through Twilio servers to REDCap. Data are stored in the REDCap database, not in Twilio, so that the data are encrypted and secured. Twilio does not maintain a log of outgoing/incoming messages or calls.

19.2 Data Procedures

All data files will be electronic, including only the unique subject ID. All datafiles will be stored on the Cancer Prevention server (\CancerPrev\CancerPrev\$\HealthBehavior\TobaccoLab). Access to this folder is restricted to authorized users. Standard protocols for data encryption (via Credant) when using laptops and USB drives will be followed.

Roswell Park Protocol Number: I 757820

19.3 Data Protocol for Multi-Site Study

All sites will input data from surveys and interviews directly into the RedCap database housed at RPCI. RPCI will conduct all data analysis.

Note: All investigator or analyzing research laboratories housing research samples need to maintain current Temperature Logs and study-specific Sample Tracking and Shipping Logs. The Principal Investigator/Laboratory Manager must ensure that the stated lab(s) have a process in place to document the receipt/processing/storage/shipping of study-related samples/specimens. This is required for all studies collecting clinical samples.

20 SAFETY REPORTING

Unanticipated Problems

An Unanticipated Problem (UP) is any incident, experience, or outcome that meets all of the following criteria:

- Unexpected (in terms of nature, severity, or frequency) given:
 - The research procedures that are described in the study-related documents, including study deviations, as well as issues related to compromise of participant privacy or confidentiality of data.
 - The characteristics of the participant population being studied.
- Related or possibly related to participation in the research (possibly related means there is a reasonable possibility that the incident, experience, or outcome may have been caused by the procedures involved in the research).

Suggests that the research places participants or others at a greater risk of harm (including physical, psychological, economic, or social harm) than was previously known or recognized and if in relation to an AE is also deemed Serious as deemed below:

Serious Adverse Events

A serious adverse event (SAE) is any adverse event (experience) that in the opinion of either the investigator or sponsor results in **ANY** of the following:

- Death
- A life-threatening adverse event (experience). Any AE that places a participant or participants, in the view of the Investigator or sponsor, at immediate risk of death from the reaction as it occurred. It does NOT include an AE that, had it occurred in a more severe form, might have caused death.
- Inpatient hospitalization or prolongation of existing hospitalization (for > 24 hours).
- A persistent or significant incapacity or substantial disruption of the ability to conduct normal life functions.
- A congenital anomaly or birth defect.
- Important Medical Event (IME) that, based upon medical judgment, may jeopardize the participant and may require medical or surgical intervention to prevent one of the outcomes listed above.

Roswell Park Protocol Number: I 757820

Reporting Unanticipated Problems

Unanticipated problem reporting will begin at the time of participant consent. The Reportable New Information (RNI) Form will be submitted to the CRS Quality Assurance (QA) Office within 1 business day of becoming aware of the Unanticipated Problem. After review, the CRS QA Office will submit the RNI to the IRB.

When becoming aware of new information about an Unanticipated Problem, submit the updated information to the CRS QA Office with an updated Reportable New Information Form. The site Investigator or designated research personnel will report all unanticipated problems to the IRB in accordance with their local institutional guidelines.

21 DATA MANAGEMENT AND CONFIDENTIALITY

21.1 Identifiable Information Necessary for Research

For purposes of this research, we will collect the following PHI:

- Participant Name – to verify identity
- Date of birth - to verify age
- Telephone number - to facilitate contact for scheduling
- Mailing address - to send study appointment materials
- Email address (optional) - to facilitate contact
- Identifiable Information protocol

Identifiable information will be retained in a separate Excel file from the analytic dataset. The only link to identifiable information will be via a unique ID number in order of participation.

All data files will be electronic, including only the unique subject ID. All data files will be stored on the Cancer Prevention server (\CancerPrev\CancerPrev\$\HealthBehavior\TobaccoLab). Access to this folder is restricted to authorized users. Standard protocols for data encryption (via Credant) when using laptops and USB drives will be followed.

Remote participation will be facilitated using videoconferencing software approved by the institution site, such as Webex, Zoom, or Microsoft Teams. All videoconferencing will be conducted using institution-affiliated logins and password protected meetings. Cisco WebEx, for which Roswell Park has a license, will be used by Roswell Park staff. This software allows for secure videoconferencing. For this study, participants will receive information to access a specific videoconference as a predetermined time with a study research assistant. Videoconferences will be recorded to confirm compliance with study procedures.

21.2 Plan to Protect Research Data

All data files will be electronic, including only the unique subject ID. All data files will be stored on the Cancer Prevention server (\CancerPrev\CancerPrev\$\HealthBehavior\TobaccoLab).

Roswell Park Protocol Number: I 757820

21.3 Data File Security

Standard protocols for data encryption (via Credant) when using laptops and USB drives will be followed.

21.4 Data File Access

Access to this folder is restricted to authorized users.

21.5 Protocol for Data Accessed by Multiple Personnel

Standard protocols for data encryption (via Credant) when using laptops and USB drives will be followed.

21.6 Plan to Destroy Identifiers

Identifiers will be deleted at the earliest possible opportunity.

21.7 Identifiable Information to be Reused or Disclosed to any Other Person or Entity

Access to this folder is restricted to authorized users.

21.8 Data Security Plan

Identifiable information will be retained in a separate Excel file from the analytic dataset. The only link to PHI will be via a unique ID number in order of participation.

All data files will be electronic, including only the unique subject ID. All datafiles will be stored on the Cancer Prevention server (\CancerPrev\CancerPrev\$\HealthBehavior\TobaccoLab). Access to this folder is restricted to authorized users. Standard protocols for data encryption (via Credant) when using laptops and USB drives will be followed.

22 STATISTICAL PLAN

22.1 Data Analysis Plan

The analysis of EMA data will be analyzed using a linear mixed model with fixed effects for vent message (product design, color/name), as well as sex and other tobacco product strata (cigarettes only or dual use). The effect of packaging will be tested using a Bonferroni-corrected type-I error rate of 0.008 (0.05/6) to account for all possible pairwise comparisons of packaging types. Data from the field-study (e.g., change in product responses, risk, TNE, aldehyde-DNA adducts) will be analyzed using linear regression with terms in the model for vent message (no message, neutral, compensation, blocking), sex, and other tobacco product use.. Categorical outcomes for the field-study will be analyzed using logistic regression. As exploratory approaches, we will use time-varying effects models (TVEMs) to explore the effect of message condition on smoking behavior (product compliance), craving, risk perception, and quit intention in the EMA data.[191, 192] TVEMs have been used previously to examine treatment effects on craving [193] and relapse.[194] TVEMs will provide daily effect sizes, thereby allowing us to examine whether treatment effects (and relationships with other predictors) change over time (i.e., early vs. later in product switching). Responses at Visit 1 can be treated as time invariant predictors and mCEQ from EMA can be treated as time-varying predictor (and/or outcome) of product use.

Roswell Park Protocol Number: I 757820

We will enroll a total sample size of 300 subjects and assume a 20% drop-out rate with uniform drop-out from Visit 1 to Visit 3. This will result in a sample size of 300 subjects for Visit 1, 270 subjects for the first week of the field study, and 240 subjects for the end of field study. Our sample size was determined to have adequate power for the field study, For the field study, we hypothesize a 25% difference between conditions, corresponding to a 3.9 CPD difference. Assuming a standard deviation of 7.6,[195] a sample size of 240 subjects will provide 95% power to detect a significant difference between ventilation conditions at the 0.05 level and 80% power to detect a significant difference between packaging conditions with a Bonferroni-corrected type-I error rate of 0.008.

mCEQ is scored using an established algorithm.⁹⁶ This results in 3 subscales (Psychological Reward, Relief, Reward) and 2 single items (Aversion, Respiratory sensation). Scores range from 1-7.

CO boost is defined as the difference between pre-smoking exhaled CO and post-smoking exhaled O. This is typically a positive value.

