1 OBJECTIVES

1.1 Purpose, Specific Aims, or Objectives

In this project, we will assess whether messaging about ventilation from cigarette filters lowers cigarette product appeal among smokers. This study, part of a series (I 50217, I 59617) will help determine whether a regulatory requirement to reduce ventilation will lower demand for cigarettes without unintended consequences. This project will assess the effect of variation in pack messaging about filter ventilation on consumers' rating of product appeal, perceptions of health risks, and changes in cigarette consumption in a 2-week field study. Our *premise* is that messaging about risks of filter ventilation will reduce the appeal of cigarette smoking and increase the likelihood that smokers would either quit smoking or switch to an alternative product (e.g., electronic cigarettes). This project is well-integrated with the other studies in this P01, using the same standardized research cigarettes with defined ventilation characteristics and design parameters, as well as relying on common biobehavioral measures.

The aim of the proposed study is to assess how adding messaging to cigarette packages about filter vents and filters influences respondents' awareness of filter ventilation, beliefs about the function of filter vents and filters, smoking behavior, ratings of cigarette satisfaction, smoking topography, exposure to nicotine and carbon monoxide, perceptions about the risk of smoking, and intention to stop smoking.⁶ The protocol will consist of a randomized experiment via two-week field study.

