3 STUDY ENDPOINTS

- Primary 1: Subjective questionnaires of product evaluation (Duke Sensory Scale, Product Evaluation Scale, Drug Effects, Hedonic Attribute), withdrawal (MNWS, QSU-B, PANAS), and readiness to quit (contemplation ladder).
- Primary 2: Number of cigarettes smoked per week during the field period.
- Secondary: Awareness and beliefs about filter ventilation and perceptions of messaging.
- Secondary: Exhaled CO is defined as level of CO measured in exhaled breath after a 15 s breathhold. This is typically 10ppm or above in daily smokers and <3 ppm in nonsmokers.
- Secondary: Smoking topography as assessed by particulate matter retained on used filters.

Roswell Park Protocol Number: I 757820

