In the event of REDCap being inaccessible for a study visit, .pdf files or paper copies of the consent will be provided to the participants and the participants will be able to sign and return or submit a photo of the signed copy.

The participant will then be randomized to 1 of 4 message conditions (No message, Neutral message, Compensation message, Blocking message) and arrangements will be made to mail, deliver, or have participants pick up study materials (study cigarettes with pack messages, CO

Roswell Park Protocol Number: I 757820

monitor, scales, butt collection materials, shipping materials, etc.). Participants will be provided with two weeks of materials.

Session 1. Session 1 will occur upon receipt of study materials by the participant. Participants will complete a baseline intake questionnaire including smoking and tobacco use history, nicotine dependence scales, SCQ, TRIRISK, delay discounting, respiratory symptoms, and knowledge, attitudes, and beliefs about filter vents. In addition, participants complete questionnaires on message perceptions (response to messaging, health risk, purchase intention) for all pack messages. Questionnaires also will be used to get baseline assessments of the user's usual brand of cigarettes (Duke Sensory Scale, Product Evaluation Scale, Hedonic Attribute Scale). Participants will be instructed to record each smoking event using the EMA app provided (described in more detail below) and to retain all spent cigarette butts and unused product. Participants will be informed that they are free to use other tobacco products (though they will not be provided as part of the study), and that these should be recorded using EMA. Participants will be provided for cigarettes for a total of two weeks, with the amount determined by normal self-reported weekly consumption rounded to nearest whole pack.

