Cigarette tracking via EMA: For the field study, the key outcome is the total number of cigarettes smoked. Participants will be asked to complete REDCap questionnaires on their personal phone (iOS or Android). Participants can use the MyCap application to respond to questionnaires. Additionally, REDCap can interface with Twilio, a secure text-messaging platform, to send study related messages and surveys via SMS (text messaging). Proposed EMA methods are based on established best practices. Participants will complete 5 questionnaires every day. These questionnaires will occur at the same time each day: 11am, 1:30pm, 4pm, 6:30pm, and 9pm. These daily reports will be used to assess cigarette and e-cigarette consumption, and 10 items relating to subjective ratings of nicotine withdrawal (e.g., craving, irritability) and mood (e.g., calm/relax, happy). At 11am only, participants will complete selected items from the Hedonic Attribute Profile and Product Evaluation Scale. At 9pm only, participants will be asked to rate the taste, satisfaction,

Roswell Park Protocol Number: I 757820

enjoyment, and craving relief from the cigarettes they smoked that day. Participants will also be asked to take a CO measurement at this time. At the 1:30 and 6:30 prompts, participants will be asked about situational factors related to use (Location, smoking permitted, with others, activity, craving) and complete the Duke Sensory Evaluation scale. Participants also will be asked to take a picture of their research cigarette pack to ensure compliance. Surveys will be open for 1 hour after the scheduled time for completion. Appendix C demonstrates the EMA schedule and the questions asked at each daily report and pseudo-random prompt. Participants can earn up to \$10 for each day of EMA compliance, with compliance being defined as responding to ≥ 4 of 5 daily prompts (up to 14 days, totaling \$140). Studies that used similar methods had $>90\%$ compliance. [189, 190].

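### Neither main model in section 22.1 has a baseline covariate, although baseline consumption and usual-brand ratings are collected; the cost is precision, of a size the documents do not fix

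*Combined protocol and SAP*

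**What the plan says.** Section 22.1 (Data Analysis Plan) describes two main models.

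- **EMA data:** a "linear mixed model with fixed effects for vent message (product design, color/name), as well as sex and other tobacco product strata".
- **Field-study data:** the examples and the method come in one sentence, "change in product responses, risk, TNE, aldehyde-DNA adducts) will be analyzed using linear regression". Its terms are message condition (four levels), sex and other tobacco product use.

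The only mention of baseline values as predictors is "Responses at Visit 1 can be treated as time invariant predictors". It comes at the end of the text on the exploratory time-varying effects models.

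Cigarettes smoked is a main outcome. Section 3 lists as Primary 2 "Number of cigarettes smoked per week during the field period", and section 11.4 says "For the field study, the key outcome is the total number of cigarettes smoked". Section 1.1 speaks of "changes in cigarette consumption in a 2-week field study".

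The baseline data exist:

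- Section 11.4 lists consumption in its block of baseline measures and covariates.
- Section 11.3 sizes the cigarette supply from usual consumption, "with the amount determined by normal self-reported weekly consumption rounded to nearest whole pack".
- Appendix C, smoking history item 13, asks average cigarettes per day.
- Section 11.3 has participants rate their usual brand at Session 1 on the Duke Sensory, Product Evaluation and Hedonic Attribute scales.

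The sample size paragraph uses a 3.9 CPD difference, "Assuming a standard deviation of 7.6".

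**The concern.** A smoker's usual daily consumption is likely to predict consumption in the next two weeks. A model without it leaves that between-person variation in the error term and widens every message comparison. Product responses do use the baseline, but only by subtraction. With equal variances at the two times, subtraction is less precise than adjustment for any r below 1.

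Width matters here because section 1.2 expects no significant effect of the messages on smoking behavior. How much a null result can tell the reader depends on the interval around it. The baseline figures are already collected, so any gain needs no more participants.

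**Working it through.** **Inputs.** From section 22.1: difference 3.9 CPD, SD 7.6, 240 analysed, alpha 0.05/6 for six pairwise comparisons. From section 11.3: four arms. Assumed: equal allocation (240/4 = 60 per arm), two-sided tests, df = 118, and 7.6 as the SD of a person's mean CPD. The correlation r is not in the documents, so 0.3 to 0.7 is shown.

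**The plan's own figure.** SE = 7.6 × √(2/60) = 1.388. The critical t at 0.05/6 is 2.683. Power for 3.9 CPD by noncentral t is 55%, against the stated 80%. Without the Bonferroni correction (alpha 0.05) it is 80%. That discrepancy is a separate matter; 55% serves here only as the unadjusted starting point.

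**Case 1: 7.6 is a raw SD.** Adjusted SD = 7.6 × √(1 − r²). Half-width = 2.683 × SD × √(2/60). The gain in equivalent sample size is 1/(1 − r²) − 1.

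| r | SD | Half-width, CPD | Half-width, per week (×7) | Power for 3.9 CPD | Equivalent extra participants |
|---|---|---|---|---|---|
| no adjustment | 7.60 | 3.72 | 26.1 | 55% | – |
| 0.3 | 7.25 | 3.55 | 24.9 | 60% | 10% |
| 0.5 | 6.58 | 3.22 | 22.6 | 71% | 33% |
| 0.6 | 6.08 | 2.98 | 20.9 | 79% | 56% |
| 0.7 | 5.43 | 2.66 | 18.6 | 89% | 96% |

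If consumption were instead analysed as change, SD = 7.6 × √(2(1 − r)). The half-widths are then 4.41, 3.72, 3.33 and 2.88 at r = 0.3, 0.5, 0.6 and 0.7. Change does no better than the unadjusted analysis until r exceeds 0.5, and it is wider than adjustment throughout.

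**Case 2: 7.6 is already a change SD.** Adjusted SD = 7.6 × √((1 + r)/2) = 6.13, 6.58, 6.80 and 7.01. The half-widths are 3.00, 3.22, 3.33 and 3.43, against 3.72 for change.

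**Case 3: 7.6 is a residual SD after baseline adjustment.** The planned precision already assumes a baseline term, so there is no gain over 3.72.

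**Product responses.** With equal variances, variance of change divided by variance after adjustment = 2(1 − r)/(1 − r²) = 2/(1 + r). This is 1.54, 1.33 and 1.18 at r = 0.3, 0.5 and 0.7, that is 54%, 33% and 18% more variance for change.

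**The case against.** The strongest reply is that section 22.1 is merely incomplete. Section 11.4 describes consumption as among the baseline measures and covariates, Appendix D repeats the description, and section 22.1 allows Visit 1 responses as predictors. This shows that the authors had baseline adjustment in view. A reader should not infer a deliberate decision to ignore baseline. But the first is a data-collection list and the second is optional and attached to exploratory models, so neither puts a term in a main model.

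Second, section 22.1 does not name the EMA model's outcome. Placing cigarettes smoked there is an inference from section 11.4. The power statement is labelled as for the field study, and with section 1.1's wording consumption might be meant as a change outcome in the regression. This stands, so the fix refers to whichever model is used.

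Third, the gain may be small. The baseline is recalled and the outcome is counted by prompt, so a high r cannot be presumed. The source cited for 7.6 is not in the reference list supplied. This also stands.

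Stronger readings are not supported:

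- **Bias.** Randomization protects both planned models, and change and adjusted analyses are both valid if the baseline is unaffected by arm.
- **The power shortfall.** A reader might blame the gap between 55% and 80% on the missing covariate. The documents do not link them. Adjustment would reach about 80% only if 7.6 is a raw SD and r is about 0.6.
- **A failed equivalence claim.** The plan sets no equivalence margin, so interval width bears on interpretation and not on a stated criterion.

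**Conclusion.** The omission is plain on the text: neither main model has a baseline covariate, and product responses use the baseline only through change. It costs precision. For cigarettes smoked, the half-width of 3.72 CPD would fall to between 3.55 and 2.66 for r from 0.3 to 0.7 if 7.6 is a raw SD, and not at all if it is a residual SD. These figures rest on equal allocation, two-sided tests, 240 completers and an assumed r. The change is worth making because the data are already collected and the cost is low. It does not undermine the validity of the planned comparisons.

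**What to change.** Amend section 22.1 as follows.

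(a) Add baseline cigarettes per day (Appendix C, smoking history item 13) as a covariate in whichever model analyses cigarettes smoked, and name that model. Item 13 is preferable to the weekly figure that sets the supply, for which the appendices show no questionnaire item.

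(b) For Duke Sensory, Product Evaluation and Hedonic Attribute, model the follow-up score on message, Session 1 usual-brand score, sex and other tobacco use, in place of change. Use the same covariate for the matching EMA items. Session 1 follows randomization and receipt of the packs (section 11.3), and the message is on the pack front (section 11.2). The usual-brand ratings should therefore come first in Session 1, before the questionnaire on all messages. This lowers the risk of early message exposure but does not remove it. If exposure shifted the Session 1 score by d between arms, change would be off by d and the adjusted analysis by r × d (equal variances), so adjustment is no worse than the plan on this point.

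(c) Leave the withdrawal measures (MNWS, QSU-B, PANAS) with the existing terms, since the section 5.1 schedule has no Session 1 score for them. Drug Effects is scheduled at Video 1 in section 5.1, but section 11.3 lists no usual-brand baseline for it. Reconcile the two before analysing it as change or with a baseline term.

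The cost is SAP wording, a line on question order in the Session 1 guide, and a few degrees of freedom.
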